7.1.2.5. Statistical Analyses/Methods

Hgb Efficacy Co-Primary Statistical Analyses
Endpoint(s)

 • Mean change in Hgb between baseline and EP
Model Specification

 • Hgb during the EP will be defined as the mean of all available post-randomization Hgb values (on and off-treatment) during the EP (Week 28-52). • The ANCOVA model used to quantify the difference in mean Hgb change will adjust for the following baseline values: 
 ○ Treatment ○ Baseline Hgb (see Section 10.5.2) ○ Current ESA use (as randomized, see Section 10.10.2) ○ Region (as randomized, see Section 10.9 & Section 10.10.2)
Multiple Imputation Analysis

 • Multiple imputation analysis will be performed using all available Hgb values (on and off-treatment) and conducted under a set of assumptions about missing Hgb values (see Section 10.6.3). 
 ○ Intermittent missing post-baseline scheduled Hgb data in both arms through Week 52 will be imputed using PROC MI procedure with NIMPUTE = 200 and MCMC IMPUTE = monotone to generate 200 datasets with only monotone missing patterns. Burn in iterations (NBITER) and maximum iteration (MAXITER) will both be set to 500. The seed for reproducibility is set to 200808. The imputations will be done by randomized treatment, current ESA use at randomization, and region. ○ For each of the monotone missing dataset (out of the 200 imputed as indicated above), the missing scheduled Hgb values through Week 52 will be imputed based on the MAR assumption and will be performed using PROC MI by treatment, current ESA use at randomization, and region. The monotone regression will have baseline Hgb, prior scheduled (possibly imputed) Hgb values, and may include current ESA use at randomization and region as covariates (see Model Checking & Diagnostics, below).

Hgb Efficacy Co-Primary Statistical Analyses

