
Hgb Efficacy Co-Primary Statistical Analyses

- The least square (LS) mean estimates and standard errors by treatment group, LS mean difference, two-sided 95% CI and one-sided non-inferiority p-value for the difference in the co-primary Hgb endpoint between the daprodustat and darbepoetin alfa arms from the ANCOVA model will be presented. The number of subjects contributing to the analysis and the associated mean and standard deviation of the baseline and EP Hgb values will also be displayed with the results of the ANCOVA model.
- The LS mean difference and associated two-sided 95% CI will be displayed on a forest plot together with supportive analysis results (excluding the Tipping Point Analysis).
- All available observed Hgb values (on and off-treatment) will be displayed graphically for each scheduled study visit using a line plot. The line plot of mean values and 95% CIs by time will include horizontal reference lines to depict the Hgb analysis range (10-11.5 g/dL), vertical reference lines to identify the EP (weeks 28-52), and the number of subjects by treatment group contributing to each mean value. The plot will be repeated by current ESA use at randomization.
 - This figure will also be repeated for visits up to and including Week 52, using the data used for the primary Hgb analysis (i.e., including imputed values). (see Section 10.6.3)).
- All available observed Hgb change from baseline values (on and off-treatment (see Section 10.6.3)) will be displayed graphically for each scheduled study visit using a line plot. The line plot of mean values and 95% CIs by time will include vertical reference lines to identify the EP (Weeks 28-52), and the number of subjects by treatment group contributing to each mean value. The plot will be repeated by current ESA use at randomization.
 - This figure will also be repeated for visits up to and including Week 52, using the data used for the primary Hgb analysis (i.e., including imputed values). (see Section 10.6.3)).
- A listing of all hemoglobin values will be provided, including treatment, most recent dose, site ID, unique subject ID, visit, assessment date, select demographic information and central laboratory and HemoCue Hgb values.

Model Results Interpretation

- Non-inferiority will be achieved if the lower limit of the two-sided 95% CI of the treatment difference is greater than the pre-specified non-inferiority margin of -0.75 g/dL.

Sensitivity Statistical Analyses

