10.10. Appendix 10: Examination of Covariates, Subgroups & Other Strata

10.10.1. Handling of Covariates, Subgroups & Other Strata

- The following is a non-exhaustive list of covariates that may be used in summaries of demographics, descriptive summaries and statistical analyses.
- Additional covariates of clinical interest may also be considered.
- If the percentage of subjects is small within a particular subgroup, then the subgroup categories may be refined prior to unblinding the trial.
- If the category cannot be refined further, then descriptive rather than statistical comparisons may be performed for the particular subgroup. If there are less than 25 subjects in one of the subgroup categories, any subgroup statistical comparison should be interpreted with caution.
- A pre-specified strategy for prioritizing subgroups/covariates is defined below (as recommended in the 2015 draft Committee for Medicinal Products for Human Use (CHMP) guidance on the investigation of subgroups in confirmatory clinical trials)
- The co-primary and principal secondary endpoints will be evaluated for the subgroups below. Although subgroup analyses are aimed to assess for consistency with the overall results, they may have low power, especially if the subgroup is small or has a low number of events. Statistical models (Cox Proportional Hazards or ANCOVA) will be adjusted for the covariates used in the original analysis, subgroup, treatment and treatment by subgroup interaction. For the prognostic randomization stratification factors (region and current ESA use), the actual status of the factor derived from the eCRF will be used (see Section 10.10.2). For the subgroup Regions combined (USA vs. non-USA), the randomization stratification factor Region (with 5 levels, Regions 1- 5) will not be included in the statistical model. For the subgroup analyses by baseline Hgb group (categorical), the baseline Hgb (continuous) will not be included in the statistical model.

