- Please note that if any of the models still fail to converge after Step 3, model-adjusted analyses will not be performed. The associated descriptive statistics will be displayed. If the original model fails to converge, but it converges after one of the three steps, the output will display the changes made to the original model in a footnote. When a subgroup category assesses the same or a similar parameter (e.g., country is similar to region) as one of the prognostic stratification variables, the randomization stratification variable will be removed from the model.
- Point estimates and two-sided 95% CIs will be estimated within subgroups, the subgroup by treatment interaction two-sided p-value will be calculated and subgroup results will be graphically presented (e.g. Forest Plots). Directional consistency in subgroup treatment effects and a non-significant interaction p-value (two-sided 10% level) would support that the overall treatment effect is broadly applicable to the full study population. Subgroup analyses will not be adjusted for multiplicity.

Category	Covariates and / or Subgroups	Summary of Demographics & Baseline Characteristics Note: Include 'Missing' categories, if applicable.	Subgroup Analysis for Co-primary MACE & Principal Secondary Safety Endpoints Note: Do not include 'Missing' categories.	Subgroup Analysis for Co-primary Hgb Endpoints Note: Do not include 'Missing' categories.
Key Covariates/Subgroups of Regulatory/Clinical Interest or Potential Biological Plausibility for Different Subgroup Effects				
Age (years)	Summary statistics of continuous values	Yes	No	No
Age at randomization (Grouping 1)	< 65 years, 65-<75 years, ≥75 years	Yes	Yes	Yes
Age at randomization (Grouping 2)	≤18 years, 19 - 64 years, ≥65 years	Yes	No	No
Age at randomization (Grouping 3)	18-64 years, 65 - 84 years, ≥ 85 years	No (included in stand-alone age ranges table)	No	No
Gender	Female, Male	Yes	Yes	Yes
Ethnicity	Hispanic or Latino, Not Hispanic or Latino	Yes	Yes	Yes
High level race	American Indian or Alaskan Native Asian Black or African American Native Hawaiian or Other Pacific Islander White Mixed Race	Yes	Yes	Yes
Race detail	American Indian or Alaskan Native Asian – Central/South Asian Heritage Asian – East Asian Heritage Asian – Japanese Heritage Asian – South East Asian Heritage	Yes	No	No

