Category	Covariates and / or Subgroups	Summary of Demographics & Baseline Characteristics Note: Include 'Missing' categories, if applicable.	Subgroup Analysis for Co-primary MACE & Principal Secondary Safety Endpoints Note: Do not include 'Missing' categories.	Subgroup Analysis for Co-primary Hgb Endpoints Note: Do not include 'Missing' categories.
	Black or African American Native Hawaiian or Other Pacific Islander White – Arabic/North African Heritage White – White/Caucasian/European Heritage Mixed Asian Race Mixed White Race Mixed Race			
Region	See Region categories defined in Section 10.9.1	Yes	Yes	Yes
Regions combined	USA, Non-USA	Yes	Yes	Yes
Country	See Countries listed in Section 10.9.1	Yes	No	No
Current ESA use at randomization	ESA non-user, ESA user, Missing	Yes	Yes	Yes
Prior ESA type at randomization	Darbepoetin alfa only, Epoetin only, Methoxy PEG-epoetin beta only, Multiple, Missing	Yes	No	No
Standardized prior ESA dose (U/week) ¹	Summary statistics of continuous values	Yes	No	No
Standardized prior ESA dose group ¹	< 3,000 U/week, ≥3,000 U/week, Missing	Yes	Yes	Yes
Baseline Hgb (g/dL)	Continuous covariate for Hgb co-primary	Yes	No	No

CONFIDENTIAL

200808

Category	Covariates and / or Subgroups	Summary of Demographics & Baseline Characteristics Note: Include 'Missing' categories, if applicable.	Subgroup Analysis for Co-primary MACE & Principal Secondary Safety Endpoints Note: Do not include 'Missing' categories.	Subgroup Analysis for Co-primary Hgb Endpoints Note: Do not include 'Missing' categories.
	analysis; summary statistics of continuous values			
Baseline Hgb group	< 9 g/dL, 9 - <10 g/dL, 10 - 11 g/dL, >11 g/dL, Missing	Yes	Yes	Yes
Baseline body mass index (kg/m ²)	Summary statistics of continuous values	Yes	No	No
Baseline body mass index group	<30 kg/m ² , ≥30 kg/m ² , Missing	Yes	Yes	Yes
Baseline weight (kg)	Summary statistics of continuous values	Yes	No	No
Baseline weight group	<75 kg, ≥75 kg, Missing	Yes	No	No
Baseline weight quartiles	Overall ITT Population Quartile 1: < xx kg Overall ITT Population Quartile 2: xx kg - < xx kg Overall ITT Population Quartile 3: xx kg - < xx kg Overall ITT Population Quartile 4: ≥ xx kg Missing	Yes	Yes	Yes
Baseline eGFR (mL/min/1.73m ²)	Summary statistics of continuous values	Yes	No	No
Baseline CKD stage (based on eGFR)	Stage 2: 60-89 mL/min/1.73m ² ; Stage 3: 30-<60 mL/min/1.73m ² ; Stage 4: 15 - <30 mL/min/1.73m ² ;	Yes	No	No

CONFIDENTIAL

200808

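### The Hgb subgroup analysis by baseline Hgb group drops continuous baseline Hgb without need, at a small cost in precision

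*SAP*

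**What the plan says.** SAP Section 7.1.2.5 defines the outcome as "Mean change in Hgb between baseline and EP" and sets the model: "The ANCOVA model used to quantify the difference in mean Hgb change will adjust for the following baseline values". The list that follows has treatment, baseline Hgb, current ESA use and region. The table in Section 10.10.1 describes baseline Hgb as "Continuous covariate for Hgb co-primary" analysis.

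For subgroups, Section 10.10.1 states the general rule: "Statistical models (Cox Proportional Hazards or ANCOVA) will be adjusted for the covariates used in the original analysis, subgroup, treatment and treatment by subgroup interaction". Two exceptions follow. For USA versus non-USA, the five-level Region factor is left out. Then: "For the subgroup analyses by baseline Hgb group (categorical), the baseline Hgb (continuous) will not be included in the statistical model". The bands are "< 9 g/dL, 9 - <10 g/dL, 10 - 11 g/dL, >11 g/dL, Missing", and the missing category is not used in the subgroup analysis. No reason is given for the second exception, and nothing elsewhere restores the covariate.

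**The concern.** Both arms are titrated to one target range, 10 to 11 g/dL (Synopsis, Study Design). A subject who starts lower therefore has further to rise, and this holds within a band as well as between bands. With bands alone, that within-band variation is left in the residual.

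The Region exception has a structural reason. Region 5 is the USA (Section 10.9.1), so the five-level factor fully determines USA versus non-USA and the terms are linearly dependent. No such dependence exists between a continuous value and a four-level grouping of it. The later rule in Section 10.10.1 that removes a similar parameter covers only the prognostic stratification variables, and baseline Hgb is not one.

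At stake is the precision of one consistency analysis. Baseline Hgb group is listed among the key subgroups of regulatory or clinical interest. Section 10.10.1 treats a non-significant interaction at the two-sided 10% level as support for broad applicability, so avoidable noise leans slightly towards the reassuring answer. The band estimates also come from a differently adjusted model than the overall estimate they are compared with.

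**Working it through.** The SAP states no precision for this analysis, so there is no figure to reproduce.

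**Inputs from the SAP.** Four bands, two of them 1 g/dL wide and two open-ended (Section 10.10.1); 4,500 subjects randomized 1:1 (Section 2.3).

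**Assumptions, not in the SAP.** Baseline Hgb normal with mean 9.9 and SD 0.7 to 1.1 g/dL; slope of change on baseline -0.5 to -1.0; residual SD 0.6 to 1.0 g/dL. Central case: baseline SD 0.9, slope -0.8, residual SD 0.8.

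**Formula.** SE ratio, bands only against bands plus continuous baseline = sqrt(1 + slope² × within-band variance / residual variance).

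**Central case.** Slope² = 0.64 and residual variance = 0.64, so the ratio reduces to sqrt(1 + within-band variance).

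| Band (g/dL) | Share | Within-band variance | SE ratio |
|---|---|---|---|
| <9 | 0.158 | 0.162 | 1.078 |
| 9 to <10 | 0.386 | 0.079 | 1.039 |
| 10 to 11 | 0.345 | 0.078 | 1.038 |
| >11 | 0.111 | 0.142 | 1.068 |

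Pooled variance: 0.158 × 0.162 + 0.386 × 0.079 + 0.345 × 0.078 + 0.111 × 0.142 = 0.099. Pooled ratio: sqrt(1.099) = 1.048. In sample-size terms, 1 - 1/1.099 = 9% of the information in this analysis. The bands already absorb 1 - 0.099/0.81 = 88% of baseline variance.

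**Range.**
- Smallest loss (baseline SD 0.7, slope -0.5, residual SD 1.0): pooled variance 0.075, sqrt(1 + 0.25 × 0.075) = 1.009.
- Largest loss (baseline SD 1.1, slope -1.0, residual SD 0.6): pooled variance 0.145, sqrt(1 + 0.145/0.36) = 1.184.
- By band: about 1% to 11% in the two middle bands and about 1% to 32% in the open-ended ones.

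**Simulation of the central case** (600 trials of 4,500, no treatment effect). Mean SEs across the four bands are 0.0629, 0.0403, 0.0426 and 0.0752 without the covariate, against 0.0600, 0.0384, 0.0406 and 0.0717 with it. That is about 5% in every band, because the ANCOVA pools one residual variance; the true sampling variability rises more in the outer bands, as in the table. Mean estimates are within 0.004 g/dL of zero in both models, so there is no systematic bias. The 95th percentile of absolute chance imbalance in baseline is about 0.03 g/dL in the middle bands and 0.06 in the outer ones. It moves the treatment difference by up to about 0.02 and 0.05 g/dL respectively.

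**The case against.** The strongest reply is that this is an explicit, prespecified choice, and that baseline Hgb is still in the model as the band effect, which carries most of the adjustment. That stands, and it is why the loss is small. It does not supply a reason for the omission.

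Three stronger readings are tempting, and the document supports none of them:
- **Bias.** A reader might infer that within-band imbalance biases the band's treatment difference. Under randomization it is chance imbalance, and its effect is the extra variance already counted above. Precision and imbalance are one cost, not two.
- **Less precise than every other subgroup.** Precision depends chiefly on subgroup size, and Section 10.10.1 allows for categories of fewer than 25 subjects. The fair comparison is with the same band analysis when the covariate is kept.
- **A threat to the main results.** The co-primary ANCOVA keeps baseline Hgb, and the MACE Cox model (Section 7.2.2) never contained it.

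A further objection has substance: keeping the covariate is not wholly free. LS means by arm are part of the Hgb output (Section 7.1.2.5). The OBSMARGINS convention in Section 10.5.3 reweights categorical variables only. With an uncentred covariate, arm means for the lowest and highest bands would be evaluated at the overall mean baseline, outside the band. Centring within band removes this and leaves the treatment contrasts unchanged.

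**Conclusion.** The point holds as a minor, optional gain in precision. The omission is not forced by collinearity and costs about 5% in standard error in the central case. The 1% to 18% pooled range rests wholly on the assumed baseline SD, slope and residual SD; the direction follows whenever change depends on baseline within a band. The upper end is probably generous, since entry Hgb is limited to 8 to 10 or 8 to 11 g/dL by ESA use (Section 2.3). A shift of at most about 0.05 g/dL in the central case is small against the requirement that the lower limit be "greater than the pre-specified non-inferiority margin of -0.75 g/dL". The scope is the baseline-Hgb-group analysis of the co-primary Hgb endpoint, run once with imputed data and once with evaluable values. Nothing here shows that a conclusion would change.

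**What to change.** Replace the sentence in Section 10.10.1 with one stating that, for the Hgb ANCOVA by baseline Hgb group, continuous baseline Hgb centred at its band mean is kept alongside baseline Hgb group, treatment and the treatment-by-group interaction, and that LS means are evaluated at a centred value of zero, so each band's arm means refer to that band's own mean baseline.

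The cost is one degree of freedom, a common slope across bands (the co-primary ANCOVA already assumes a single slope) and the LS-means convention above. No new data are needed.

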10.10.2. Randomization Stratification

Randomization is stratified by current ESA use, region and by participation in an ABPM sub-study to ensure balance across treatment groups for both the overall parent study and within the ABPM sub-study. The prognostic stratification factors (i.e., current ESA use and region) will be taken into account within the analysis models. Stratification by ABPM sub-study participation was implemented for logistical reasons, and will not be taken into account within analysis models.

Baseline current ESA use strata will be identified by two data sources:

- PPD's IRT dataset
- eCRF

The proposed approach is to use the IRT strata in the adjusted analysis models in order to provide a randomization-based test statistic in accordance with the principle of 'analyze as randomized'. In summaries of subgroups however, the actual status of the factor for stratification derived from the eCRF form will be used.

10.11. Appendix 11: Multiple Comparisons & Multiplicity

10.11.1. Handling of Multiple Comparisons & Multiplicity

[figure not shown]
10.11.1.1. Interim Analyses

The interim analysis will only result in stopping the study for harm or futility. There are no prospectively defined plans to stop any of the ASCEND trials early for benefit. As such, no multiplicity adjustments are required since the type I error rate will not be increased. Further details including stopping guidelines for harm and futility are included in the IDMC charter.

10.11.1.2. Final Analyses

The multiplicity strategy for this trial will use a combination of a gatekeeper approach on the co-primary endpoints, followed by a closed-test multiplicity procedure wrapped around the family of principal secondary analyses.

[Figure 1](#) illustrates the structure of the statistical testing plan. First, the co-primary endpoints will be evaluated for at least non-inferiority by comparing each two-sided 95% CI to the appropriate non-inferiority margin. Then, the principal secondary analyses will be performed, and superiority will be tested for the individual analyses. Conditional on both co-primary endpoints achieving non-inferiority (i.e., passing the gatekeeper), the family of principal secondary analyses will be formally tested for superiority using the widely known Holm-Bonferroni procedure [[Holm, 1979](#)]. The procedure will be conducted based on a family-wise Type I error rate set at the one-sided 2.5% level.

Figure 1 Multiplicity controlled statistical testing plan**Details of the Holm-Bonferroni procedure for testing secondary endpoints:**

The procedure starts with conducting the statistical analyses for each of the principal secondary analyses and ranking the resulting one-sided p-values from most significant (i.e. the lowest p-value) to the least significant. The Holm-Bonferroni formula is calculated for each rank using a target alpha. The formula for the Holm-Bonferroni method is:

[figure not shown]
$$\text{Holm - Bonferroni}_i = \frac{\text{Target } \alpha}{n - \text{rank}_i + 1}$$

Where:

- the *target α* is the overall alpha level (one-sided 2.5% significance)
- *n* is the total number of tests

The most significant p-value is compared to the rank-associated alpha derived from the Holm-Bonferroni method. If a positive statistically significant treatment effect is observed, then the testing continues to the next ranked test. If the endpoint fails to achieve statistical significance when compared to the Holm-Bonferroni rank-associated alpha, the testing stops and all subsequent endpoints are declared to have failed to achieve statistical significance. This algorithm is described in detail in [Figure 2](#) for the four principal secondary analyses defined for the trial.

Figure 2 The Holm-Bonferroni Procedure for Multiplicity Control

10.11.1.3. Subgroup Analyses

Subgroup analyses will not be adjusted for multiplicity.

10.12. Appendix 12: Model Checking and Diagnostics for Statistical Analyses

10.12.1. Statistical Analysis Assumptions

Endpoint(s)	
 Hgb Change from Baseline to the EP
Analysis	
 ANCOVA
	
 Distributional assumptions underlying the model used for analysis will be examined by obtaining a normal probability plot of the residuals and a plot of the residuals versus the fitted values (i.e. checking the normality assumption and constant variance assumption of the model respectively) to gain confidence that the model assumptions are reasonable. If there are any departures from the distributional assumptions, alternative models will be explored using appropriate transformed data. Models will be examined for treatment interactions with baseline Hgb and stratification factors
Analysis	
 Multiple Imputation/Tipping Point Analysis
	
 Intermittent missing data imputation: 
 If there are error and or warning messages related to the by statement (e.g. not enough observations to fit regression models), try to impute by randomized treatment and current ESA use at randomization, then by randomized treatment only until no error/warning messages. If convergence issue still occurs, the convergence precision may be set to 1E-3. Monotone missing data imputation: 
 When imputing for each of the monotone missing dataset (out of the 200), if there are error and or warning messages related to the by statement and/or regression model (e.g. not enough observations with the Monotone statement), try 1) impute by randomized treatment and current ESA use at randomization, with baseline Hgb and region as covariates, 2) impute by randomized treatment, with baseline Hgb, current ESA use at randomization, and region as covariates, 3) impute by randomized treatment, with baseline Hgb, and current ESA use at randomization as covariates, 4) impute by randomized treatment with baseline Hgb as a covariate, until no error/warning messages.
Endpoint(s)	
 Time to first event endpoints: MACE and MACE or thromboembolic events or hospitalization for HF
Analysis	
 Cox proportional hazards
	
 To inform on the validity of the adjusted Cox proportional hazards model, the proportional hazards assumption will be assessed by plotting the logarithm of the negative logarithm of the estimated survivor function against the logarithm of time, for each treatment group, region and current ESA use at randomization. If the hazards are proportional, the lines should be approximately parallel. Should there be evidence of a violation of the proportional hazards assumption, the following methods may be considered: 
 Use of a stratified Cox proportional hazards model (including prognostic factors in a STRATA statement in PROC PHREG, rather than in the MODEL statement)
Endpoint(s)	
 Time to first event endpoints with death as a competing risk

Analysis	
• Cox proportional hazards

• If there is a notable difference between one or both of all-cause mortality and non-CV mortality, and one or more of the secondary CV endpoints that do not include death as a component, then additional analysis methods to address competing risks may be pursued such as:
○ Fine & Gray's Subdistribution Hazards [Fine, 1999]○ Use of cumulative incidence functions instead of KM curves	

